4.2. Statistical endpoints and independent variables

The present protocol is a prospective, multicenter registry with the goal to observe and analyse multidisciplinary treatment approaches in childhood-onset craniopharyngioma. Therefore, several endpoints were chosen that reflect patients' survival and QoL. The association between these endpoints and a set of independent variables that represent diagnostic characteristics and treatment strategies will be analysed. On the basis of previous analyses (e.g., KRANIOPHARYNGEOM 2000 / KRANIOPHARYNGEOM 2007), the independent variables have been divided into two categories according to their expected influence on outcome and prognosis of childhood-onset craniopharyngioma.

Endpoints: - Overall survival (OS) defined as time from diagnosis to death

- Progression-free survival (PFS) defined as time from diagnosis to progression or death (whichever occurs first)
- Quality of life (PedQol, PedsQL, FMH)
- Degree of obesity (BMI SDS)

Factors of influence (mandatory):

- Tumor location (grade of hypothalamic involvement, grade 0-2)
- Neurosurgical treatment strategy (intended radical resection vs.
- incomplete resection + XRT)
- Realized degree of surgical resection (complete resection vs. incomplete resection)
- Postsurgical hypothalamic lesions (grade 0-2)
- Irradiation: modality (photon vs. proton beam therapy) and treatment (dose)

Factors of influence (potential):

- Clinical manifestations and symptoms in history
- Duration of history
- Histology (adamantinomatous vs. papillary type)
- Hydrocephalus at diagnosis
- Patient load of treating neurosurgical units (based on patient load during 10 yrs)
- Patient load of treating radiotherapy units (based on patient load dring 5 or 10 yrs)
- Tumor structure in imaging (tumor volume, cysts, calcifications)
- Endocrine deficiencies (number of deficient hypothalamic-pituitary axes)
- Growth hormone substitution (patient age at initiation, duration)
- Ophthalmological deficits (visual acuity, perimetric deficits)
- Neuropsychological findings, memory deficits, cognition (HIT-Basisdiagnostikum)

- Eating disorders (IEG)
- Experimental therapeutic approaches for obesity treatment (GLP-1R Agonists, Oxytocin)
- Other experimental therapeutic approaches, e.g. intracavitary therapy (intracystic IFN- α)

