4.3. Statistical analysis

The analysis of the data collected in this registry will be mainly descriptive. All inferential analyses will be regarded as exploratory (hypotheses generating) and will be interpreted accordingly. The aim of the analyses is to describe the frequency and modality of treatment approaches and to investigate their influence on survival and QoL. Since the planned study is a purely observational study, no randomized comparisons of treatment strategies are possible. Therefore, in addition to univariable analyses, multivariable analysis strategies are used to take account of different baseline risks due to different demographic or diagnostic characteristics. The model selection in the mutivariable analyses can be done by clinical considerations or by means of automated selection as likelihood-ratio based stepwise selection procedures.

Continuous variables (e.g., BMI SDS, QoL) will be summarised using the following descriptive statistics: n (non-missing sample size), number of missing values, mean, standard deviation, median, Q25%, Q75%, maximum and minimum. Histograms or boxplots will be used for graphical presentation of data. For the comparison of independent groups, statistical tests appropriate to the statistical distribution of the particular endpoint will be used (e.g., Student's t-test, Mann-Whintey U-test). To assess the difference of measurements between two different time points, statistical tests as Student's t-test for paired samples, Wilcoxon signed-rank test, or the sign-test will be applied. For comparison of more than two successive measurements, methods accounting for intra-individual correlation will be used (e.g., Linear Mixed Models), additionally adjusting for potential confounders.

Time-to-event endpoints as OS and PFS will be analysed descriptively using the Kaplan-Meier method. Groups will be compared using the log-rank test. Multivariable analyses will be performed using Cox proportional hazard regression analysis.

For categorical variables, the frequency and percentages (based on the non-missing sample size) of observed levels will be reported. Bar charts will be used for graphical presentation of data. The association of a categorical outcome and categorical independent variables will be analyszed using Fishr's exact test or the χ^2 test.

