6.4. Proposed preoperative neuroradiological imaging

Magnetic resonance imaging (MRI)

Cerebral MRI with and without contrast enhancement is the preferred neuroradiological technology for for primary diagnosis of childhood brain tumors. The following **MRI sequences** are proposed:

Before gadolinium enhancement injection:

- T1-weighted sagittal and coronary images (max. 3–4 mm thick slices)
- Proton-weighted and T2-weighted axial images of the entire brain

After gadolinium enhancement:

- T1-weighted images, coronary and sagittal, as taken in pre-contrast enhancement images
- T1-weighted axial images as done for T2

Computerized tomography (CT) of the sellar area

CT is specifically used to identify calcifications frequently found in craniopharyngiomas. Because calcifications are **not** detectable in MRI, identifying their existence and location using CT is absolutely key to planning of surgical access and operative approaches. Another essential use of CT is the differential diagnostic assessment of craniopharyngioma vs. astrocytoma by calcification verification. For the reasons just described, preoperative CT verification of calcification localization is a highly proposed diagnostic consideration.

As a rule, postoperative native, non-enhanced CT monitoring should be carried out so that any eventual residual tumor calcifications can be identified. If preoperative CT has definitively ruled out the existence of calcifications, postoperative CT can be waived. Early postoperative MRI (within first 48 to 72 hours) is not required as craniopharyngioma are extraaxial cerebral tumors. First postoperative MRI for assessment of residual tumor and the degree of resection should be performd 2-3 month after initial surgery.

For routine follow-up monitoring, MRI **without** contrast agent (gadolinium) is recommended. When MRI is not available, CT without contrast agent can be used on a very exceptional basis for follow-up course monitoring. However, the cumulative lens dosage in follow-up CT examinations needs to be paid close attention to.

Original images of the following examination series should, along with the local radiologist findings, be sent to the KRANIOPHARYNGEOM Registry 2019 neuroradiology reference center (Department of Neuroradiology, Dr. [name], Universitätsklinikum Augsburg) via telematic platform:

- Preoperative MRI and CT
- Postoperative MRI and CT if used (depending on preoperative calcification verification)

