Every participating clinic, in collaboration with a pediatric endocrinologist, should make every effort to provide continuing follow-up care for patients whose age is far beyond the pediatric age group. Evaluating long-term consequences of treatment and disease is also an important goal of KRANIOPHARYNGEOM Registry 2019. It is therefore imperative that at the beginning of treatment, an assessment be made of the numerous diagnostic results regarding the patient's anthropometric, endocrine, ophthalmologic, intellectual, and psychological status (see section: Preoperative diagnostics).

Long-term diagnostic and therapy standardization, evaluation and quality control were chief aims of HIT-ENDO and KRANIOPHARYNGEOM 2000/2007 and are also goals of KRANIOPHARYNGEOM Registry 2019. The following goals have been set in order to develop a long-term care program in accordance with recently published guidelines for follow-up care in patients with pediatric oncological diseases (AWMF guideline):

- standardization of endocrine diagnostics and substitution therapy
- quality control of endocrine, imaging, ophthalmological and neuropsychological follow-up diagnostics
- quality control of hormonal substitution therapy

Data acquisition regarding postoperative endocrine substitution therapy is limited. Hormone substitution dosage data is not included in the scope of KRANIOPHARYNGEOM Registry 2019. Data acquisition is restricted to which hormone axis requires substitution.

Radiooncological follow-up (as required by radiation protection legislation)

All patient examinations must be systematically monitored once a yr by a radiooncologist. The corresponding documentation forms should be filled out and sent to the radiation reference center.

Treatment-associated long-term consequences of radiation therapy for malignant diseases in children and adolescents

Coordinator:[name]. med. [name], Medizinische Hochschule Hannover, Strahlentherapie und spezielle Onkologie, [name], [contact], [contact], E-mail: [contact]

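### OS and PFS run from diagnosis, but growth hormone use and duration, obesity drugs, intracystic therapy and irradiation begin later; as fixed factors in log-rank or Cox analyses they carry immortal-time bias

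*Protocol*

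**What the plan says.** Protocol section 4.2 sets the time origin for both survival endpoints: "Overall survival (OS) defined as time from diagnosis to death" and "Progression-free survival (PFS) defined as time from diagnosis to progression or death (whichever occurs first". It then commits to relating the endpoints to the listed factors: "The association between these endpoints and a set of independent variables that represent diagnostic characteristics and treatment strategies will be analysed".

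Several of those factors are treatments given after diagnosis:

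- Mandatory: "Irradiation: modality (photon vs. proton beam therapy) and treatment (dose", and a neurosurgical strategy whose second level combines incomplete resection with irradiation.
- Potential: "Growth hormone substitution (patient age at initiation, duration", GLP-1R agonists or oxytocin for obesity, and intracystic therapy.

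Section 4.3 specifies Kaplan-Meier curves and the log-rank test for groups, and continues: "Multivariable analyses will be performed using Cox proportional hazard regression analysis". It gives differing baseline risk as the reason for multivariable modelling and calls all inference exploratory. Neither section mentions a time-dependent covariate, a landmark, delayed entry or a later time origin.

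On data collection, section 9 says of postoperative hormone substitution: "Data acquisition is restricted to which hormone axis requires substitution". The table in section 8.11 provides for annual documentation of hormonal therapy, naming growth hormone, on CRF 5.

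**The concern.** A log-rank test, or a Cox model with a fixed covariate, treats group membership as known at time zero. These memberships are not. A patient who dies before starting growth hormone is counted as untreated; a patient who starts at two years contributes two years to the treated group during which, by construction, no death could occur. The untreated group collects the early deaths and the treated group collects guaranteed survival time.

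Growth hormone duration is the plainest case. It can never exceed the time from start to death or censoring, so as a fixed covariate it partly restates the outcome.

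Adjusting for baseline characteristics does not help, because the error lies in how person-time is allocated and not in who the patients were at diagnosis. At stake is the registry's aim of learning how treatments influence survival: an ineffective treatment can appear strongly protective.

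**Working it through.** **Timing of the factors, from the protocol.** Section 6.8 advises against growth hormone substitution before surgery and puts stimulation tests 6 months after it. Section 3.1 places the largest BMI increase in the first 12 months after diagnosis or surgery, so obesity drugs come during or after that period. Section 2.8.1.1 describes irradiation as either immediate or contingent on progression. All of these fall after time zero.

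**No design figure to reproduce.** The protocol states no event count, power or effect size, so the size of the bias has to be illustrated under a true hazard ratio of 1.

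**Main scenario (OS, growth hormone).**

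- Death rate from the 87% ten-year OS in section 2.3: -ln(0.87)/10 = 0.0139 per year, constant.
- Follow-up uniform over 0-10 years (assumed).
- 80% would receive growth hormone (assumed; section 2.11.1.1 puts post-treatment deficiency at about 70-92%).
- Start at 0.5 year plus an exponential delay with mean 1, 2 or 3 years (assumed).

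| Coding | Apparent HR for OS (truth 1.0) |
|---|---|
| Ever treated, fixed | about 0.34-0.42 |
| Treated, start-stop | about 0.97-1.04 |
| Duration, fixed, treated patients only | 0.43, 0.56, 0.62 per year (mean delay 1, 2, 3 years) |
| Duration, fixed, all patients (untreated = 0) | about 0.72 per year |

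Repeat runs differ by several hundredths.

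**Sensitivity to assumptions.** With complete ten-year follow-up in place of uniform censoring, fixed ever-treated gives 0.56, 0.39 and 0.37 for the three delays. With OS following the 93/91/87% at 3/5/10 years in section 2.3, complete ten-year follow-up and 70% or 92% candidates:

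- start at 0.5-1 year: fixed 0.66 or 0.32; time-dependent 1.06 or 0.95;
- start at 0.5-3 years: fixed 0.44 or 0.16; time-dependent 1.11 or 1.00.

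In this setting fixed duration among treated patients gives 0.14 per year or lower, so the duration figure depends heavily on follow-up and start times. Its direction does not.

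**PFS.** Assume five-year PFS of 40-80%, a post-diagnosis treatment in 50%, and only treatment begun before the event counted. Fixed coding gives 0.88-0.96 for starts at 0.15-0.5 year, 0.73-0.84 for 0.5-1 year and 0.56-0.70 for 0.5-3 years. Time-dependent coding gives 0.97-1.05.

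**Resection and lesion grade.** Section 6.4: "First postoperative MRI for assessment of residual tumor and the degree of resection should be performd 2-3 month after initial surgery". The share lost before that MRI is small:

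- deaths: 1 - 0.93^(2/36) = 0.4% to 1 - 0.93^(3/36) = 0.6%;
- PFS events: 1 - 0.80^(2/60) = 0.7% to 1 - 0.40^(3/60) = 4.5%, over the assumed five-year PFS range.

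**Photon versus proton among irradiated patients** (assumed five-year PFS 60%). Equal delays of 0.3 year give HR 1.00. Delays of 0.3 versus 0.6 year give 0.96, and 0.3 versus 1.0 year give 0.89. Delayed entry at the start of irradiation restores 1.00-1.01.

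**The case against.** The strongest reply is that the protocol never says these factors will be time-fixed. Cox regression accepts time-dependent covariates, and their coding is commonly left to a SAP, which may exist. That is fair as far as it goes. But the protocol itself fixes diagnosis as the origin, names log-rank for groups, lists total growth hormone duration as a factor, and justifies the models by baseline risk alone. Followed as written, that gives a wrong answer, so this is more than missing detail.

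A second reply is that the registry is mainly descriptive, all inference is exploratory, growth hormone and obesity drugs are only potential factors, and QoL and BMI SDS do not suffer this bias in the same form. This stands, and it lowers the severity. It does not remove a systematic error from the OS and PFS analyses.

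Three stronger readings are tempting and are not supported:

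- A reader might infer that every factor recorded after diagnosis is seriously affected. Resection and lesion grade are set by surgery and merely measured at 2-3 months; photon versus proton is distorted only when delays differ.
- A reader might infer that every such treatment will look protective. Irradiation given at progression follows the PFS event; if it is counted as exposure, the bias may run the other way.
- A reader might infer from section 9 that growth hormone dates are not recorded. Section 8.11 documents growth hormone therapy annually and the forms are not shown. What is shown is that sections 4.2, 8.11 and 9 do not agree.

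**Conclusion.** The point holds for growth hormone use and duration, obesity drugs, intracystic therapy, and irradiated versus not irradiated, including the combined resection-and-irradiation strategy and dose counted from zero. For these, log-rank groups or fixed Cox covariates measured from diagnosis carry immortal-time bias.

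For growth hormone and OS, the spurious hazard ratio is about 0.34-0.42 in the main scenario, against about 1.0 with start-stop coding. Across the other start times, treated shares and follow-up patterns it ranged from 0.16 to 0.66. Treatment start times, treated shares, follow-up and PFS rates are assumptions, so the figures show direction and rough size and do not predict the registry's results. The bias is smaller for early-starting treatments, was smaller in the PFS scenarios run, and is negligible for resection and lesion grade.

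Severity is moderate: the error is systematic and potentially large, but no confirmatory conclusion depends on it.

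**What to change.** In section 4.3, for OS and PFS:

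1. Enter treatments that start after diagnosis as time-dependent covariates in start-stop form, or use a stated landmark with patients alive and event-free at that point, in place of log-rank groups fixed at diagnosis.
2. Compare photon with proton from the start of irradiation, using delayed entry.
3. Do not use total growth hormone duration as a fixed covariate.
4. For PFS, do not count irradiation given at or after progression as exposure before the event.

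Reconcile section 4.2 (age at initiation and duration of growth hormone), section 8.11 (annual documentation of hormonal therapy) and section 9 (only which axis is substituted). If the factor is kept, growth hormone start and stop dates must be captured; no dose is needed.

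The cost is a few sentences, slightly more analysis work, any events lost before a landmark and, if not already on the forms, two date fields. The date question is best settled while recruitment is open, since an analysis plan cannot recover dates that were never collected.

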4.3. Statistical analysis

The analysis of the data collected in this registry will be mainly descriptive. All inferential analyses will be regarded as exploratory (hypotheses generating) and will be interpreted accordingly. The aim of the analyses is to describe the frequency and modality of treatment approaches and to investigate their influence on survival and QoL. Since the planned study is a purely observational study, no randomized comparisons of treatment strategies are possible. Therefore, in addition to univariable analyses, multivariable analysis strategies are used to take account of different baseline risks due to different demographic or diagnostic characteristics. The model selection in the mutivariable analyses can be done by clinical considerations or by means of automated selection as likelihood-ratio based stepwise selection procedures.

Continuous variables (e.g., BMI SDS, QoL) will be summarised using the following descriptive statistics: n (non-missing sample size), number of missing values, mean, standard deviation, median, Q25%, Q75%, maximum and minimum. Histograms or boxplots will be used for graphical presentation of data. For the comparison of independent groups, statistical tests appropriate to the statistical distribution of the particular endpoint will be used (e.g., Student's t-test, Mann-Whintey U-test). To assess the difference of measurements between two different time points, statistical tests as Student's t-test for paired samples, Wilcoxon signed-rank test, or the sign-test will be applied. For comparison of more than two successive measurements, methods accounting for intra-individual correlation will be used (e.g., Linear Mixed Models), additionally adjusting for potential confounders.

Time-to-event endpoints as OS and PFS will be analysed descriptively using the Kaplan-Meier method. Groups will be compared using the log-rank test. Multivariable analyses will be performed using Cox proportional hazard regression analysis.

For categorical variables, the frequency and percentages (based on the non-missing sample size) of observed levels will be reported. Bar charts will be used for graphical presentation of data. The association of a categorical outcome and categorical independent variables will be analyszed using Fishr's exact test or the χ^2 test.

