- **Topic:** Childhood-onset craniopharyngioma, xanthogranuloma, cysts of Rathke's pouch, meningioma, pituitary adenoma, arachnoid cysts
- Objectives: Collect epidemiological information
 - Collect information on treatment and outcome to determine whether a relationship exists between outcomes and specific interventions
 - Collect information on late effects and QoL
 - Assess the quality of treatment by the means of data collection, data check and an advisory service provided by the registry and the reference centers
 - Establishment of a tumor bank as a base for further biological studies to define new molecular risk factors and to identify new targets for therapy

Expected case numbers:

- 30 craniopharyngioma patients/yr
- 10 patients with other sellar masses/yr
- Endpoints: Overall survival (OS)
 - Progression-free survival (PFS)
 - Quality of life (PedQol, PedsQL, FMH)
 - Degree of obesity (BMI SDS)

Factors of influence (mandatory):

- Tumor location (grade of hypothalamic involvement, grade 0-2)
- Neurosurgical treatment strategy (intended radical resection vs. incomplete resection + XRT)
- Realized degree of surgical resection (complete resection vs. incomplete resection)
- Postsurgical hypothalamic lesions (grade 0-2)
- Irradiation: modality (photon vs. proton beam therapy) and treatment (dose)

Factors of influence (potential):

- Clinical manifestations and symptoms in history
- Duration of history
- Histology (adamantinomatous vs. papillary type)
- Hydrocephalus at diagnosis
- Patient load of treating neurosurgical units (based on patient load during 10 yrs)
- Tumor structure in imaging (total volume, cysts, calcifications)
- Endocrine deficiencies (number of deficient hypothalamic-pituitary axes)
- Growth hormone substitution (patient age at initiation, duration)
- Ophthalmological deficits (visual acuity, perimetric deficits)
- Neuropsychological findings, memory deficits, cognition (HIT-Basisdiagnostikum)
- Eating disorders (IEG)
- Experimental therapeutic approaches for obesity treatment
- (GLP-1R Agonists, Oxytocin)
- Other therapeutic approaches, i.e. intracavitary therapy (intracystic interferone α (INF- α))

Inclusion criteria:

Confirmed histological diagnosis of craniopharyngioma, xanthogranuloma, cysts of Rathke's pouch, meningioma, pituitary adenoma or arachnoid cysts in patients ≤18 yrs by reference pathology.

Informed consent by legal guardians and/or patient to contribute data to the registry.

Exclusion criteria:

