2.3. Epidemiology

Craniopharyngioma is the most common nonglial intracranial tumor in the pediatric population with an incidence rate of 0.5–2 per million people per yr, 30 to 50% cases of whom are children and adolescents. Craniopharyngiomas constitute 1.2 to 4% of all pediatric intracranial tumors. The incidence rate is concentrated among two age groups with peaks in children 5 to 10 yrs of age and adults 50 to 75 yrs of age [20]. Craniopharyngiomas are systematically recorded by the German Pediatric Cancer Registry (DKKR) in accordance with international guidelines. Between 1980 and 2001, 385 craniopharyngioma patients under the age of 18 were identified and registered. Of that total, 345 diagnosed patients were <15 yrs of age. The median age at the time of diagnosis was 8.6 yrs in this under 15-yrs-of-age patient group (sex ratio 1:1). Their overal survival rate was 93% after 3 yrs of observation, 91% after 5 yrs, and 87% after 10 yrs of observation. Patients who were diagnosed and treated in the 1980s had a lower survival rate probability (p<0.05) than patients who were diagnosed and treated in the 1990s (5-yr survival rate probability: 88% vs. 96% respectively) [4].

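### Section 4.3 permits stepwise selection for adjusted treatment comparisons without keeping the mandatory factors in the model; the instability is worst for overall survival

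*Protocol*

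**What the plan says.** Section 4.2 lists 5 mandatory and 14 potential factors of influence, 19 in all. It bases the split on the influence expected from earlier studies. It does not say that mandatory factors must stay in every model.

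Section 4.3 notes that randomised comparisons are impossible and brings in multivariable models to allow for differing baseline risks. OS and progression-free survival (PFS) are to be analysed by Cox regression. The model may be chosen on clinical grounds or "by means of automated selection as likelihood-ratio based stepwise selection procedures". No entry or removal threshold is given, and the option is not limited by endpoint or number of events. The same section calls the analysis mainly descriptive and all inference exploratory.

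The Synopsis expects "30 craniopharyngioma patients/yr" and "10 patients with other sellar masses/yr". For German registry patients under 15 years of age, Section 2.3 gives OS of "93% after 3 yrs of observation, 91% after 5 yrs, and 87% after 10 yrs of observation", and by decade of diagnosis (1980s against 1990s) a "5-yr survival rate probability: 88% vs. 96% respectively".

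**The concern.** The models are there to adjust for confounding. Likelihood-ratio stepwise selection asks a different question, namely whether a variable improves fit enough to pass a p-value threshold. A confounder with a moderate effect can fail that test in a small sample and still bias the treatment comparison once it is left out. Hypothalamic involvement is the clear example. The protocol's own summary of the KRANIOPHARYNGEOM 2000 results ranks it as the leading risk factor for poor long-term prognosis, and Section 2.11.1.13 reports an effect on 20-year OS, yet a model built as Section 4.3 allows could compare surgical strategies without it.

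Standard output after a stepwise search also treats the final model as if it had been fixed in advance. P-values are then too small, intervals too narrow and the selected effects too large. What is at stake is the credibility of adjusted comparisons of surgery and irradiation, and of the hypotheses the registry is meant to generate.

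**Working it through.** The protocol states no sample size, event count or power, so there is no figure of its own to reproduce.

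**1. Multiplicity of the search.** Assume a 5% entry level (the protocol gives none) and 19 independent null candidates:

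1 − 0.95^19 = 0.62.

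This does not depend on the number of deaths. Several listed factors hold more than one variable (tumour structure, for example, covers volume, cysts and calcifications), so 19 is a lower bound on the candidates.

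**2. Expected deaths.** Assume uniform accrual of 30 a year, administrative censoring only, and survival interpolated linearly through 1, 0.93, 0.91 and 0.87 at 0, 3, 5 and 10 years. Deaths by year T are 30 × ∫₀ᵀ [1 − S(t)] dt.

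- Years 0–3: 3 × 0.035 = 0.105
- Years 3–5: 2 × 0.08 = 0.16
- Years 5–10: 5 × 0.11 = 0.55
- By year 5: 30 × 0.265 = 7.95
- By year 10: 30 × 0.815 = 24.45

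Log-linear interpolation gives 7.99 and 24.51.

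| Scenario | Deaths, 5 yrs | Deaths, 10 yrs |
|---|---|---|
| 30/yr, full-series OS | 8 | 24–25 |
| 30/yr, 5-yr OS 96% | 3 | 12 |
| 30/yr, 5-yr OS 88% | 9 | 30 |
| 40/yr (all sellar masses), full-series OS | 10.6 | 32.6 |

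The 96% and 88% rows assume the same relative decline from year 5 to year 10 as the full series (0.87/0.91).

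**3. Deaths per factor and per parameter.**

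- Per listed factor: 7.95/19 = 0.42 and 24.45/19 = 1.3.
- Mandatory factors alone need 6 parameters if the two 0–2 grades are entered as ordered scores (two grades, strategy, resection, modality, dose): 1.3 and 4.1 deaths per parameter.
- With the grades as categories they need 8: 1.0 and 3.1.

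**4. Power to keep a true factor.** For a balanced binary factor at two-sided 5%, power = Φ(½√d × ln HR − 1.96). For HR 2 this is 16% with 8 deaths and 40% with 24. The HR needed for 80% power is exp[2.80/(½√d)]: 7.3 with 8 deaths and 3.1 with 24.

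**5. Inflation of what is selected.** By the same approximation, a balanced binary factor considered alone reaches p < 0.05 only if |ln HR| > 3.92/√d. With 8 deaths that is 1.386, an estimated HR of at least 4.0 (or at most 1/4.0). With 24 deaths it is 0.80, an HR of at least 2.2. A true HR of 2 can therefore enter at that step only if it is overestimated.

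**6. Simulation under assumed conditions.** Stepwise Cox selection was simulated with entry p < 0.05, removal p > 0.10, 19 binary factors with the 5 mandatory ones correlated, and 200 runs per scenario.

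| | About 8 deaths | About 24 deaths |
|---|---|---|
| At least one null potential factor selected | 50–63% | 55–58% |
| True HR 2 mandatory factor kept | 18–25% | 34–49% |
| Null potential factors as share of selections, some mandatory effects real | 47–59% | 35–42% |
| Same share, no mandatory effect real | 76% | 78% |

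The first row barely changes with the number of deaths, which fits step 1. The second row is where scarcity of deaths shows.

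**The case against.** Stepwise selection is only one of two routes, and the clinical route is named first. All inference is exploratory, and no decision hangs on a stepwise OS model. Entry thresholds and candidate sets usually belong in a statistical analysis plan, which is not shown. All of this lowers the severity. But the protocol itself states the selection method, and an exploratory label neither restores a dropped confounder nor widens an interval that ignores the search.

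The horizons of 5 and 10 years are assumptions, since the protocol fixes no analysis date. It also continues follow-up of patients from the earlier studies, and Section 2.11.1.7 mentions 485 registry patients. If those were pooled at 13% ten-year mortality (an assumption), 485 × 0.13 ≈ 63 deaths would be added. With the 24 to 25 new ones that is about 87.5/19 ≈ 4.6 per listed factor. Whether they are pooled is not stated. This objection stands as a limit on the death counts.

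Several stronger readings are tempting and not supported:

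- *That selected OS models would be mostly noise.* At about 24 deaths with some real mandatory effects, null potential factors make up 35–42% of selections. Section 4.2 chose the factors from earlier analyses, so some real effects are plausible.
- *That the 62% reflects too few deaths.* It is plain multiplicity.
- *That the plan contradicts itself by calling factors mandatory.* Section 4.2 sorts factors by expected influence and states no retention rule, so this is a missing safeguard.
- *That the shortage affects every endpoint.* It concerns OS. Quality of life and BMI SDS do not depend on deaths, and Section 2.8.1.1 cites progression in 71–90% after incomplete resection.

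**Conclusion.** The concern holds as a defect of method, of moderate severity. Followed as written, Section 4.3 can produce adjusted treatment comparisons without the factors Section 4.2 calls mandatory, and with p-values and intervals that ignore the search. This applies to every endpoint for which stepwise selection is used. The chance of at least one false selection is about 62% under 19 independent null candidates and a 5% entry level, both assumed.

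OS is the worst case, with about 8 deaths after 5 years and 24 to 25 after 10 from new craniopharyngioma accrual, or about 3 and 12 with 5-year OS of 96%. The 93/91/87% figures come from patients diagnosed between 1980 and 2001, so better current survival would give fewer deaths. Pooling earlier cohorts would give more. At these counts a true HR of 2 is more often missed than kept, and factors that enter tend to carry inflated hazard ratios. The retention figures depend on the simulated effect sizes and thresholds, none of which the protocol specifies.

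**What to change.** In Section 4.3, delete automated selection for adjusted treatment comparisons. Alternatively, allow it only among the potential factors, with the mandatory factors forced in and bootstrap selection stability reported. Use a fixed, clinically chosen covariate set that includes the mandatory confounders for the comparison at hand. Add potential factors to that set one at a time and report all of them with intervals, whether or not they reach significance.

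For OS, fit the fixed set with Firth or ridge-penalised Cox regression, or report Kaplan-Meier estimates only while deaths are too few. A cap of two or three OS covariates is not a good substitute, because it would itself leave out most mandatory factors. State also whether patients from the earlier studies are pooled, since that determines the number of deaths available.

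The cost is a few sentences in Section 4.3, with no new data and no change to conduct. The downside is fewer, or shrunken, OS estimates in early reports.
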